13. SUBJECT WITHDRAWALS

Current, state, federal, and institutional regulations concerning informed consent will be followed. Participation in this study is voluntary. Participants are free not to take part or to withdraw at any time, for whatever reason, without risking loss of present or future care they would otherwise expect to receive. In the event that a patient does withdraw from the study, the information they have already provided will be kept in a confidential manner. Participants may discontinue participation in the study at any time if they decide they do not wish to take part any longer. Participants may be withdrawn from the study by research personnel if it is deemed in their best interest to no longer participate.

14. PRIVACY AND CONFIDENTIALITY OF SUBJECTS AND RESEARCH DATA

All intervention sessions and follow-up interviews will be recorded using digital audio recorders. Following systematic transfer from the digital recorders to a password-protected computer and backup on secure drives

hosted at URMC, the digital files will be erased. All audio recorders and transcripts will be kept in locked file cabinets in locked research offices of the study coordinator at URMC.

The study team will assign a numerical Study ID to each participant once they have signed the consent form. Study forms and questionnaires will use this number and the participant's first and last initials as identifiers to ensure data integrity. Other identifying information will not exist on these forms. A complete list of study participants with study ID, name, and contact information will be maintained separately for the purpose of contacting participants for research or study-related updates; this database will be maintained until the study is closed. This linkage information will only be accessible to the PI, study investigators, and the individual responsible for maintaining the database.

Additionally, the data can be collected and managed by the research teams at University of Rochester Medical Center using REDCap electronic data capture tools hosted at URMC.

URMC provides the following information on the REDCap program: "Vanderbilt University, in collaboration with a consortium of institutional partners, has developed a software toolset and workflow methodology for electronic collection and management of research and clinical trial data, called REDCap (Research Electronic Data Capture). The REDCap system is a secure, web-based application that is flexible enough to be used for a variety of types of research. It provides an intuitive interface for users to enter data and real time validation rules (with automated data type and range checks) at the time of data entry. REDCap offers easy data manipulation with audit trails and functionality for reporting, monitoring and querying patient records, as well as an automated export mechanism to common statistical packages (SPSS, SAS, Stata, R/S-Plus). Through the REDCap Consortium, Vanderbilt has disseminated REDCap for use around the world

All data collected for the current study will be used in post hoc analyses as appropriate. Overall study results will be presented to participants, faculty and staff at the University of Rochester Medical Center after completion of the study. Study results will be presented at professional meetings and published.

15. DATA AND SAFETY MONITORING PLAN

15.1 AE/SAE Definitions

- The following definitions are used in this DSMP and are consistent with the NIA's Adverse Event and Serious Adverse Event Guidelines and the University of Rochester's Research Study Review Board (RSRB) policies:
- An adverse event (AE) is any untoward or unfavorable medical occurrence (both physical and psychological) in a human subject, including any abnormal sign (for example, suicide ideation), symptom, or disease, temporally associated with the subject's participation in the research, whether or not the AE is considered related to the subject's participation in the research.
- A serious adverse event (SAE) is an event that (per OHRP guidelines) that:
 1. results in death;
 2. is life-threatening (places the subject at immediate risk of death from the event as it occurred);
 3. results in inpatient hospitalization or prolongation of existing

hospitalization;

4. results in a persistent or significant disability/incapacity; or
5. Is another condition that investigators judge to represent significant hazards.

- An unanticipated problem (UP) is any incident, experience, or outcome that meets all of the following criteria:
 1. unexpected, in terms of nature, severity, or frequency, given (a) the research procedures that are described in the protocol-related documents, such as the IRB-approved research protocol and informed consent document; and (b) the characteristics of the study population;
 2. related or possibly related to participation in the research (possibly related means there is a reasonable possibility that the incident, experience, or outcome may have been caused by the procedures involved in the research);
 3. suggests that the research places participants or others at a greater risk of harm (including physical, psychological, economic, or social harm) than was previously known or recognized.

Note: The vast majority of adverse events occurring in human subjects are not unanticipated problems. A small proportion of adverse events are unanticipated problems. Unanticipated problems include other incidents, experiences, and outcomes that are not adverse events.

16.2 Classification of Severity and Study Relatedness

Adequate review, assessment, and monitoring of adverse events requires they be classified as to severity, expectedness, and potential relatedness to the study intervention. This section includes descriptions of how adverse events will be classified in these domains, as these classifications determine the reporting requirements.

Severity classifications are as follows:

- Mild: Awareness of signs or symptoms, but easily tolerated and are of minor irritant type causing no loss of time from normal activities. Symptoms do not require therapy or a medical evaluation; signs and symptoms are transient.
- Moderate: Events introduce a low level of inconvenience or concern to the participant and may interfere with daily activities, but are usually improved by simple therapeutic measures; moderate experiences may cause some interference with functioning.
- Severe: Events interrupt the participant's normal daily activities and generally require systemic drug therapy or other treatment; they are usually incapacitating.

Note: Severity is not synonymous with seriousness. Severe anxiety is not likely to be an SAE, for example. Likewise, a severe headache is not necessarily an SAE. However, mild chest pain may result in a day's hospitalization and thus is an SAE.

Expectedness is a key dimension in classifying adverse events. AEs must be assessed as to whether they were expected to occur or unexpected, meaning not anticipated based on current knowledge found in the protocol, investigator brochure, and informed consent document. Categories are:

- Unexpected - nature or severity of the event is not consistent with information about the condition under study or intervention in the protocol, consent form, or investigator brochure.

- Expected - event is known to be associated with the intervention or condition under study.

For the current study, the following are expected AEs and SAEs based on the study population and behavioral intervention under investigation. The study population is characterized by older age, caregiver stress, and social disconnectedness. The intervention is a six-session group behavioral intervention delivered via video conferencing that involves learning behavioral skills to promote positive social experiences in one's life in the context of caregiving demands.

- Expected AEs are:
 - Increased stress, anxiety, worry, depressive symptoms, and other forms of emotional distress (including suicide ideation) may occur in some participants due to the nature of thinking about stressors in one's life;
- Expected SAEs are:
 - Hospitalization due to physical and/or psychological factors;
 - Suicide attempts;
 - Deaths due to natural causes

Relatedness is another key dimension in classifying adverse events. The potential event relationship to the study intervention and/or participation will be assessed by the PI and Co-I's. Categorizations are as follows:

- Definitely Related: The adverse event is clearly related to the behavioral intervention or assessment procedures – i.e. an event that follows a reasonable temporal sequence from administration of the study intervention, follows a known or expected response pattern to the suspected intervention, that is confirmed by improvement on stopping and reappearance of the event on repeated exposure and that could not be reasonably explained by the known characteristics of the subject's clinical state.
- Possibly Related: An adverse event that follows a reasonable temporal sequence from administration of the study intervention follows a known or expected response pattern to the suspected intervention, but that could readily have been produced by a number of other factors.
- Not Related: The adverse event is clearly not related to the investigational intervention/procedure - i.e. another cause of the event is most plausible; and/or a clinically plausible temporal sequence is inconsistent with the onset of the event and the study intervention and/or a causal relationship is considered biologically implausible.

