9. RISKS TO SUBJECTS

The potential risks to study participants are minimal for all procedures. For research assessments (self-report questionnaires and semi-structured interviews), the primary risks are invasion of privacy, breach of confidentiality (if safety issues are detected), or mild reactions of distress or fatigue. All assessment measures and procedures have been safely used previous research with older adults; no sustained negative effects from assessments are expected, but negative outcomes cannot be ruled out. For the DLR intervention, the primary risks are emotional distress or fatigue and potential loss of privacy. Regarding distress and fatigue, subjects may think about stressors, negative life events, and caregiving burden/distress; they will receive support from the interventionist for such experiences. No sustained negative effects are expected, but negative outcomes from behavioral interventions cannot be ruled out. Regarding privacy, given the videoconferencing modality, participants will be given information upfront about risks to privacy and instructed on actions they can take to protect their privacy.

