16.3 AE/SAE Reporting

This study is a minimal risk study adapting and refining a behavioral intervention. This section describes the study team's process for identifying AEs and SAEs, collecting information regarding the events, and reporting procedures. All AEs will be documented on an Adverse Event Form (electronic format) and stored in the regulatory file. An Adverse Event log may also be kept. Study staff will notify the study PI of an adverse event as soon as possible—at the latest by the end of the day in which the event was discovered. The PI has the final decision regarding what is to be reported on the adverse event form and has the option to reclassify an AE as a serious adverse event (SAE). All AEs experienced by the participant during the time frame specified in the protocol (e.g., from the start of intervention through the end of the study) are to be reported.

All adverse events, regardless of their seriousness, severity or relatedness to the intervention are reportable to NIA PO and STAR Center Pilot Core Directors, and the University of Rochester Institutional Review Board.

The following reporting schedule will be adhered to:

- Adverse events and serious adverse events that are not deemed “related and unexpected” will be reported to: the STAR Center MPIs (Drs. [name] & [name]) at the next regularly scheduled meeting (held monthly at a minimum); the STAR Center Pilot Core Directors quarterly; the IRB per IRB policies, at a minimum, annually at the time of continuing review; the NIA Program Officer quarterly (or more often as deemed necessary by the STAR Center Pilot Core Directors).
- If SAEs occur that are unexpected (i.e., not listed in the Data and Safety Monitoring Plan), they will be reported to the STAR Center MPI’s, the NIA Program Officer, the IRB, and to the STAR Center Pilot Core Directors within 48 hours of study’s knowledge of SAE. The expedited report will be followed by a detailed, written SAE report as soon as possible. Note that follow up information may be required and asked for by the independent safety monitoring body directly, or through the NIA or its representative.
- Unexpected deaths, that is, deaths not due to natural causes will be reported to the STAR Center MPI’s, the NIA Program Officer, the IRB, and to the STAR Center Pilot Core Directors within 24 hours of study’s knowledge of death.

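### A non-fatal suicide attempt or psychiatric admission judged related to DLR has no required 48-hour SAE report, because both are on the expected-SAE list

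*Combined protocol and SAP*

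**What the plan says.** Three parts of the data and safety monitoring plan combine here.

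- **The list.** Section 16.2 (Classification of Severity and Study Relatedness) names three expected SAEs: "Hospitalization due to physical and/or psychological factors", "Suicide attempts" and "Deaths due to natural causes". None is limited by cause or by relation to the intervention. An expected event is defined there as one where the "event is known to be associated with the intervention or condition under study".
- **The expedited rule.** Section 16.3 (AE/SAE Reporting) reads: "If SAEs occur that are unexpected (i.e., not listed in the Data and Safety Monitoring Plan), they will be reported to the STAR Center" MPIs, and it continues with the NIA Program Officer, the IRB and the Pilot Core Directors, all within 48 hours.
- **The routine rule.** Also in 16.3, any AE or SAE not deemed both related and unexpected goes to the MPIs at their next meeting (at least monthly), to the Pilot Core Directors quarterly, to the NIA Program Officer quarterly or more often if those Directors think it necessary, and to "the IRB per IRB policies, at a minimum, annually at the time of continuing review".

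Deaths from other than natural causes have their own 24-hour rule. Unanticipated problems that may raise participants' risk go to the Pilot Core Directors, the IRB and NIA within 48 hours.

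**The concern.** Whether an SAE is reported quickly to anyone outside the study team turns on whether its type is on a list. The list contains the two kinds of serious non-fatal event that one would most want seen early if life review were to cause severe distress: a suicide attempt and a psychiatric admission. The hospitalization entry excludes no cause, so it covers every admission.

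The list also appears to have been written for another study. The paragraph that introduces it describes a group program of six sessions teaching behavioral skills. Section 4.2 describes eight sessions of life review with one patient and one caregiver.

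What is at stake is the timing of outside review. There is no DSMB (16.5), and Pilot Core leadership meets twice a year (16.5.1). The PI and co-investigators judge relatedness (16.2), and the PI may also deliver the sessions (2.3 and 4.2). In that setting, prompt independent sight of a related event matters more than usual, because further dyads may enroll in the meantime.

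**Working it through.** No plan figure needs reproducing. The check is to send each type of SAE through the rules of 16.3, using the list and definitions of 15.1 and 16.2.

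| Event | On the list? | Routine rule (not both related and unexpected) | 48-hour rule (not listed) | Result |
|---|---|---|---|---|
| Hospitalization, related | yes | applies | does not apply | routine |
| Non-fatal suicide attempt, related | yes | applies | does not apply | routine |
| Either of these, unrelated | yes | applies | does not apply | routine |
| Natural death | yes | applies | does not apply | routine |
| Completed suicide | no | set aside by the death rule | set aside by the death rule | 24 hours |
| Other SAE, related | no | does not apply | applies | 48 hours |
| Other SAE, unrelated | no | applies | applies | the rules conflict |

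**Relatedness does not rescue a listed event.** The definition of expected includes events associated with the intervention itself, and the 48-hour trigger glosses unexpected as not listed. In the first two rows, listing alone decides.

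**The last row is a separate inconsistency.** The routine rule takes everything that is not both related and unexpected. The 48-hour rule asks only whether the event is unexpected. An unlisted SAE judged unrelated satisfies both, and the section does not say which governs.

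**Longest stated interval on the routine route, against 14 weeks of participation (7.7):**

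- MPIs, at least monthly: 52 / 12 = about 4.3 weeks.
- Pilot Core Directors and NIA, quarterly: 52 / 4 = 13 weeks, nearly the whole of one participant's time in the study.
- IRB, the protocol's own minimum: 52 weeks, and 52 / 14 = about 3.7 times one participant's time in the study.

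The allowance for earlier reporting to NIA belongs to the Pilot Core Directors, whose own report on this route is quarterly.

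**The unanticipated-problem route.** Section 15.1 requires the event to be unexpected in nature, severity or frequency, given the procedures described in the protocol documents and the population. It does not refer to the list. Section 9 gives the main DLR risks as emotional distress or fatigue and loss of privacy, and adds: "No sustained negative effects are expected, but negative outcomes from behavioral interventions cannot be ruled out". On that basis a related attempt could be called unexpected in severity. Yet the protocol also lists attempts as expected, which makes the opposite judgment equally easy to defend for a single event. The outcome is left to the investigator.

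**The case against.** The best case for the plan is that the delay affects external reporting only, and that several safeguards remain. Study staff tell the PI on the day an event is discovered. Active suicidal ideation triggers immediate review and consideration of emergency psychiatric services (16.4). Every adverse event is reportable to NIA, the Pilot Core Directors and the IRB, whatever its relatedness. Completed suicide is expedited. In patients aged 65 or over with Stage III or IV cancer, admissions and natural deaths are foreseeable, and listing them avoids a stream of uninformative urgent reports. All of this stands, and it limits the point to when outside bodies learn of related, non-fatal events.

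It also rules out some stronger readings that a reader might infer:

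- **That the unanticipated-problem route is closed to listed events.** It is not. Its test is nature, severity or frequency, so it is uncertain.
- **That the IRB would wait a year.** A year is the protocol's minimum. IRB policy governs, is not in the documents, and may be faster.
- **That such events escape all prompt oversight.** Same-day notice to the PI contradicts this.
- **That the list contradicts section 9 or the minimal-risk basis for the consent waiver in section 7.** The list is said to reflect the population as well as the intervention, and events arising from age and illness can be expected without the procedures being risky.

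What the objection does not supply is a required 48-hour SAE report for a listed event judged related to DLR.

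**Conclusion.** The concern holds in this form: under 16.2 and 16.3 as written, a non-fatal suicide attempt or a psychiatric admission judged related to DLR takes the routine route. The stated interval moves from 48 hours to as much as a month for the MPIs and a quarter for the Pilot Core Directors and, unless they ask for more, NIA. For the IRB it becomes whatever its policies require, with a year as the outer limit in the protocol. Two textual faults add to this: the list rests on a description of a different intervention, and the two SAE triggers disagree for unlisted, unrelated events.

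The conclusion assumes that the gloss in 16.3 is meant literally, so that listing decides expectedness, and that no unseen IRB policy sets a shorter time. It does not assume that DLR causes such events; the documents give no rate for them. No endpoint or analysis is affected. In a single-arm pilot of 40 dyads, this should be fixed, but it does not undermine the study.

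**What to change.** 1. **In 16.2**, replace the description of the six-session group program with DLR, and rewrite the expected list for this intervention and population. Suicide attempts, and hospitalizations judged related to DLR, should not count as expected merely because the event type is listed. Admissions explained by cancer, its treatment or existing illness can stay on the list.
2. **In 16.3**, reconcile the two triggers. An SAE judged possibly or definitely related should get expedited external reporting whether or not it is listed, and the text should say which route an unlisted, unrelated SAE takes.

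With the second change, prompt reporting of a related SAE no longer depends on how the unanticipated-problem test is read. Ordinary unrelated admissions stay on the routine route. The changes affect reporting only, not participants' care. The cost is revised safety-plan wording and a few more expedited reports.

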16.3 AE/SAE Reporting

This study is a minimal risk study adapting and refining a behavioral intervention. This section describes the study team's process for identifying AEs and SAEs, collecting information regarding the events, and reporting procedures. All AEs will be documented on an Adverse Event Form (electronic format) and stored in the regulatory file. An Adverse Event log may also be kept. Study staff will notify the study PI of an adverse event as soon as possible—at the latest by the end of the day in which the event was discovered. The PI has the final decision regarding what is to be reported on the adverse event form and has the option to reclassify an AE as a serious adverse event (SAE). All AEs experienced by the participant during the time frame specified in the protocol (e.g., from the start of intervention through the end of the study) are to be reported.

All adverse events, regardless of their seriousness, severity or relatedness to the intervention are reportable to NIA PO and STAR Center Pilot Core Directors, and the University of Rochester Institutional Review Board.

The following reporting schedule will be adhered to:

- Adverse events and serious adverse events that are not deemed “related and unexpected” will be reported to: the STAR Center MPIs (Drs. [name] & [name]) at the next regularly scheduled meeting (held monthly at a minimum); the STAR Center Pilot Core Directors quarterly; the IRB per IRB policies, at a minimum, annually at the time of continuing review; the NIA Program Officer quarterly (or more often as deemed necessary by the STAR Center Pilot Core Directors).
- If SAEs occur that are unexpected (i.e., not listed in the Data and Safety Monitoring Plan), they will be reported to the STAR Center MPI’s, the NIA Program Officer, the IRB, and to the STAR Center Pilot Core Directors within 48 hours of study’s knowledge of SAE. The expedited report will be followed by a detailed, written SAE report as soon as possible. Note that follow up information may be required and asked for by the independent safety monitoring body directly, or through the NIA or its representative.
- Unexpected deaths, that is, deaths not due to natural causes will be reported to the STAR Center MPI’s, the NIA Program Officer, the IRB, and to the STAR Center Pilot Core Directors within 24 hours of study’s knowledge of death.
- Unanticipated problems that do not indicate increased risk to participants, will be reported to the IRB and NIA within 10 calendar days of identifying the problem. Unanticipated problems that may cause increased risk to participants will be reported to the STAR Center Pilot Core Directors, the IRB, and NIA within 48 hours of identifying the problem. The Unanticipated Problems report must include a corrective plan and measures to prevent reoccurrence. Reports of Unanticipated Problems, as defined above, will be forwarded to OHRP using [contact], within two weeks of the event.

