3. ADMINISTRATIVE ORGANIZATION

Research locations:

3.1 The setting of this study will be Wilmot Cancer Institute (WCI) and Highland hospital. The WCI and Highland hospital site is the largest provider of cancer care across 16 counties in upstate New York. The WCI has an established infrastructure for conducting clinical research. WCI provides sources of collaboration, research training programs, weekly grand round presentations, and highly productive special interest research groups.

3.2 Rochester Roybal Center for Social Ties and Aging Research: The Rochester Roybal Center for Social Ties and Aging is funded through an NIH P30 grant and National Institute of Aging with the mission to support the development of behavioral interventions targeting the improvement of social connectedness for caregivers of family members with dementia. The Roybal Center will provide STAR resources to support caregiver assessments.

3.3 DLR participation will take place through video-conferencing. Participants will be encouraged to participate from their home or other private location. Wherever the location may be, the PI or other trained licensed mental health clinicians who are conducting the DLR intervention will ensure privacy in a private room with a closed door. Participants will be provided with a HIPAA compliant tablet to use for participation in the intervention activities and the intervention will be delivered using HIPAA compliant video-conferencing technology provided by the University of Rochester. The coordinator will be in touch with patients by phone throughout the length of the study. The study coordinator will help organize the scheduling/rescheduling of baseline assessments, DLR session, and follow-up assessments and interviews, and will be available for any patient or caregiver questions.

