Semi-Structured Interviews: The in-depth interviews with the patients and caregivers (interviewed separately) will focus on patient and caregiver experiences before, during, and after the telehealth DLR intervention. Patients and caregivers will be interviewed separately to ensure that each partner has a chance to disclose feelings and experiences without being censored by the other partner. Interview transcripts for a dyad will be compared later to establish common themes.

8.2 Study Procedures:

- **After Informed Consent:** Immediately after informed consent, the UBACC will be administered to determine capacity to consent. the study coordinator or PI will provide patients and caregivers with a HRV device to bring home. If patients are unable to bring the HRV device home, study staff will mail HRV device to patient/caregiver with return address envelope. This is an exploratory aim to explore the feasibility of collecting HRV with older patients and caregivers in this way. Patients and caregivers will then return the

HRV device at their next clinic visit or mail back in provided return address mailer.

- Heart Rate Variability Collection (HRV): Study staff will coordinate a zoom call with the patient and caregiver to demonstrate how to use the HRV device. Patient and caregivers will each take turns using the HRV device. Patients and caregivers will separately follow the following procedures when wearing the HRV device:
 - set timer for 20 minutes
 - sit in comfortable position
 - quiet space with no distractions
 - dimly lit room
 - no use of phone or any devices
 - maintain normal breathing

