16. "Is there any other feedback about the intervention you would like to provide?"

Dyadic Life Review Intervention Guide:

Session 1: Childhood

Welcome and thank you for your time today. Today we will be focusing on each of your childhood experiences. I will have some questions to help us get started with our conversation. There is no right or wrong response. You are free to move through memories as they come and I [the interventionist] may prompt for more detail or information as you recall these events.

[Direct questions to first patient then the caregiver, when possible use patient and caregivers' names to support building rapport through this process]

1. How are you feeling today?
2. Let's take a minute and have your minds take you back to your childhood, birth through 13. Tell me a memory that first comes to your mind?
 - 2a. [Caregiver] What did this memory [Patient] just share make you feel or think about?
What was the first memory that came to mind for you [caregiver]?
 - 2b. [Patient] What did this memory [Caregiver] just share make you feel or think about?
3. Who was most influential in your life during this period?
 - 3a. [Caregiver] What did this memory [Patient] just share make you feel or think about?
Who was most influential for you in your childhood [caregiver]?
 - 3b. [Patient] What did this memory [Caregiver] just share make you feel or think about?
4. Tell me about your favorite place during childhood?
 - 4a. [Caregiver] What did this memory [Patient] just share make you feel or think about?
Tell me, [Caregiver] about your favorite place during childhood?
 - 4b. [Patient] What did this memory [Caregiver] just share make you feel or think about?

Session 2: Adolescence

Welcome and thank you for your time today. Today we will be focusing on each of your adolescent experiences. I will have some questions to help us get started with our conversation. There is no right or wrong response. You are free to move through memories as they come and I [the interventionist] may prompt for more detail or information as you recall these events.

[Direct questions to first patient then the caregiver, when possible use patient and caregivers' names to support building rapport through this process]

1. How are you feeling today?
2. Let's take a minute and have your minds take you back to your adolescence. Tell me a memory that first comes to your mind from this period of your life?

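### Section 16.3 promises a process for identifying adverse events but never has anyone ask about them; the only scripted wellbeing prompt during the 8 weeks is put with the partner present, so distress events are likely to be under-recorded or found late

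*Combined protocol and SAP*

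**What the plan says.** Section 16.3 (AE/SAE Reporting) states that it describes the study team's "process for identifying AEs and SAEs, collecting information regarding the events, and reporting procedures". The text that follows requires all events to go on an electronic AE form, allows an optional log, requires staff to tell the PI "at the latest by the end of the day in which the event was discovered", leaves classification to the PI, and sets reporting timelines. The collection window is given only as an example: "e.g., from the start of intervention through the end of the study".

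The safety section on classification (16.2, Classification of Severity and Study Relatedness) lists the expected adverse events: "Increased stress, anxiety, worry, depressive symptoms, and other forms of emotional distress (including suicide ideation) may occur in some participants".

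The intervention is eight weekly joint video sessions. Item 1 in every session of the Dyadic Life Review Intervention Guide is "How are you feeling today", and the guide directs questions to the patient and then to the caregiver on the same call.

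Outside the sessions, section 3.3 says: "The coordinator will be in touch with patients by phone throughout the length of the study". The tasks it goes on to list are scheduling and answering questions from patients or caregivers.

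The exit interviews are held separately for patient and caregiver. Section 8.1 gives the reason: "to ensure that each partner has a chance to disclose feelings and experiences without being censored by the other partner".

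**The concern.** A section that announces how adverse events are identified should say who asks, what is asked, how often and of whom. Section 16.3 starts at the point where an event has already been discovered.

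The omission matters more here than in many small behavioural studies. The events the plan expects are mostly internal states, which staff will not see unless the person shows or reports them. The weekly contact at which they might come up is one where the other half of the dyad is listening. A patient may not want to tell a caregiver that the sessions have made things worse, and the reverse holds too.

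Two things are at stake. One is participant safety: a person who worsens early may have no scheduled private check until the follow-up period. The other is how the adverse-event record is read by those who oversee the study. A low count cannot be told apart from non-disclosure.

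**Working it through.** The documents give no adverse-event rate or detection rate, so there is no figure to reproduce. The check is to go through each place where an asking step could sit and see whether one is there.

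1. **Section 16.3.** It covers documentation, notice to the PI, classification and reporting. It names no question, instrument, interval or asker.
2. **Questionnaires (8.1).** The Distress Thermometer, Geriatric Depression Scale, PROMIS29, Perceived Stress Scale and Interpersonal Needs Questionnaire are given at baseline and after the intervention only. Participants may complete them on their own in REDCap, so staff need not be present. No rule says when a worse score becomes an adverse event.
3. **Sessions (Intervention Guide).** The wellbeing question opens all eight sessions with both partners on the call. It is a conversational opening and is not described as an adverse-event check. Section 8.2 gives fidelity as the purpose of recording the sessions.
4. **Safety provisions (16.4, and 7.3).** Observation for distress or fatigue by the research coordinator is tied to assessment interviews. The immediate safety evaluation covers both assessments and sessions, but begins when a concern arises. The further suicide-risk questions begin when ideation is endorsed. All of these are reactive.
5. **Coordinator contact (3.3).** There is no call schedule and no adverse-event question. The sentence on phone contact names patients; caregivers appear as people who may bring questions.
6. **Exit interview script.** It asks about dislikes, limitations, memories the person would rather not share, coping and loneliness. No item asks whether the person was harmed or got worse.

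Next, set the expected events (16.2) beside the reason for separate interviews (8.1). The plan accepts that a partner can inhibit disclosure of feelings, and it guards against this when collecting feedback. It has no matching step when collecting harms, although the expected harms are feelings.

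**Timing.** Section 8.2 puts follow-up in weeks 9-10. For someone who worsens in week 2 and does not say so in a session, the first scheduled private contact comes 9 − 2 = 7 to 10 − 2 = 8 weeks later. If the problem has passed by then, nothing in the plan requires anyone to ask about it.

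**People affected.** 40 dyads × 2 = 80 participants.

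**The case against.** The strongest reply is that the plan is not blind to distress. Licensed mental health clinicians run every session, may adapt it to expressed needs, and support participants who become distressed. Research coordinators are trained in a safety protocol that uses Columbia scale items and clinical interview. That protocol is not part of these documents, so how actively it asks cannot be judged. After the intervention each person completes several distress measures and is interviewed alone, inside the example collection window. Hospitalisation and death do not depend on what someone says in front of a partner. The study is also described as minimal risk.

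Most of this stands, and it rules out several stronger statements a reader might infer:

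- **That 16.4 applies only to assessment interviews.** It does not; it also covers concerns that arise in sessions.
- **That the coordinator serves patients only.** Section 3.3 makes the coordinator available for caregiver questions too.
- **That adverse-event counts rest wholly on joint sessions.** The post-intervention measures and separate interviews are a second route, though a later one.
- **That the trial will carry a biased safety estimate into the next study.** No aim or analysis estimates an adverse-event rate. The sample size section carries the quantitative data forward for sample size planning only.

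What the reply does not supply is an asking step. Each safeguard depends on the participant volunteering a problem, visibly showing one, or still scoring badly weeks later. Minimal-risk status does not remove the task that 16.3 sets itself.

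**Conclusion.** The point holds in a limited form. Section 16.3 announces an identification process and does not give one, and no other section fills the gap during the 8 weeks. For distress, depressive symptoms and suicide ideation, detection as written is passive and mostly in the partner's presence. Under-recording or late detection is therefore likely, but it is an inference. It rests on one assumption, which section 8.1 shares: that some people disclose less when the partner is listening.

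A reader might want to attach a figure, for example by assuming a disclosure fraction and inflating an upper confidence bound. The documents do not support this. They give no disclosure fraction or event rate, and such a calculation would ignore the post-intervention route. The direction is supported; the size is unknown.

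This is a gap worth closing by amendment. It is not a reason to doubt the feasibility aims, and no figure in the plan changes.

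**What to change.** Add an asking step to 16.3. Each partner is asked the same short, standard adverse-event question alone:

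- **(a)** at the separate post-intervention interview, covering the period since the start of the intervention; and
- **(b)** at one brief mid-intervention phone contact from the coordinator, made to both patient and caregiver.

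Answers are recorded on the existing AE form and follow the notification and reporting steps already in 16.3. The change concerns ascertainment only and leaves the plan's clinical responses as they are.

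**Cost.** A short script and a wording change. Part (a) adds a few minutes to interviews that are already held separately. Part (b) means up to 80 short calls (40 patients and 40 caregivers). Not all of these are scheduled now: existing patient contacts can be used where they occur, but the plan schedules no mid-intervention call to caregivers. More mild events will be recorded. No new staff or visits are needed.
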